In the pilot testing phase, 66 HIV+ PWID and their treatment support partners (n=66) will participate in a pilot randomized controlled trial (RCT) of the adapted couple-based intervention developed in the pre-trial phase of the study. Psychologists and intervention facilitators will be trained to deliver the adapted intervention remotely to assess safety, feasibility, acceptability, retention, and preliminary estimates of adherence to directly inform a future, full-scale R01 efficacy trial. Couples will be randomized to the intervention or standard of care (SOC) arms and assessed with repeated measures at four time-points on ART adherence, behavioral outcomes (i.e., drug use, sexual risk behavior), social support processes, and biological measures from baseline to 6 months post-intervention (see **Table 2** below). Electronic monitoring device (EMD) and weekly mobile app data will be collected throughout the intervention and follow-up periods. Due to COVID-19, all study procedures will be conducted remotely.

4.3. Study location and Recruitment Sites. HIV+ PWID will be recruited from the Almaty AIDS Center, which has 1,546 patients on ART, 660 of whom are PWID prescribed ART at least 6 months, 240 of whom are not virally suppressed.⁴⁶ Current AIDS Center patients on ART are 57.6% male and 42.4% female.⁴⁶ The AIDS Center does not currently provide any routine adherence intervention to patients, but recognizes ART adherence as a significant problem and is highly motivated to conduct research and intervention adaptation with us.

4.3.1. Recruitment and Eligibility Screening. Participants will be recruited from the Almaty City AIDS Center. An epidemiologist at the Almaty City AIDS center will review patient records to determine which patients potentially meet eligibility requirements. A list of potentially eligible patients will be given to nurses at the Almaty City AIDS Center. Nurses will call patients to inform them about the study and, for those who are interested, conduct eligibility screening with them. The nurse will obtain consent from eligible participants to be contacted by research staff and provide research staff with the contact information of eligible participants who have consented to be contacted.

[figure not shown]

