Research staff will call eligible participants and explain the study verbally in detail, including the purpose of the study and the study procedures (including risks and benefits) and will answer questions to ensure that the patient understands what would be expected of her/him. The RA will then conduct confirmatory eligibility screening and informed consent. If the participant is eligible, the RA will send the participant a Qualtrics link to complete the baseline assessment. The RA will also obtain participant consent to review recent viral load test results from the AIDS Center and medical/research records. Potential participants will be told that participation in this study is completely voluntary and their decision whether or not to participate in this study or provide permission for screening will not affect any medical treatment they are receiving at the clinic or their participation in any other studies.

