4.6.3. Immediately Post-Intervention (IPI) Visit (for all participants)

The IPI will be conducted by phone/video call or in-person in GHRCCA’s field office (post-COVID). Prior to the visit, an RA will mail an IPI kit to participants containing materials to self-collect hair and urine samples. For in-person visits, participants will self-collect samples at the GHRCCA field office. The following procedures/assessments will be performed at the IPI visit:

1. The RA will verify the participants by the name on the record and update the **Locator Information Form**;
2. The RA will send the **IPI Assessment** through Qualtrics;
3. The RA will conduct an **EMD** test and will check in with the participant regarding EMD uses and resolve any issues;
4. Participants will self-collect urine samples and hair samples to measure biological levels of medication adherence. These samples will be mailed to GHRCCA staff.
5. At the participant’s next regular AIDS Center visit, the nurse will obtain an additional **blood sample** to conduct dried blood spot sampling and measure levels of medication in the body

4.6.4. 3-month and 6-month Follow-Up Visits (for all participants)

Three- and six-month Follow-Up Visits will be conducted by phone/video call or in-person in GHRCCA’s field office (post-COVID). The following procedures/assessments will be performed at the 3- and 6-month follow-up visits:

1. The RA will verify the participants by the name on the record and update the **Locator Information Form**;
2. The RA will send the **3- or 6-month follow-up assessment** through Qualtrics;
3. At the **3-month** follow-up, the RA will conduct an **EMD** test and will check in with the participant regarding EMD uses and resolve any issues. At the **6-month** follow-up, the participant will mail the **EMD** back to the RA.
4. After the **6-month** follow-up, the RA will administer the Exit Interview;

4.6.5. Pilot study assessments. Participants in both arms will receive the same schedule of assessments. There will be four main repeated assessment occasions: baseline “pre-intervention”, immediately post-intervention (IPI), 3-month and 6-month follow-up. The primary adherence outcome will be proportion of prescribed doses taken as measured by EMD. Study assessments will be delivered remotely through Qualtrics.

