All other data will be labeled only with the PID and will not contain any identifiable information. All data from source 2 (assessment data) will be collected electronically on password protected and encrypted tablets. Data on the tablets will be electronically transmitted to a secure, remote and HIPAA compliant server with partitioned and dedicated space for this study only, known as the 'study server'. Only authorized users will be able to log into the server to view and download data for analysis. The server will maintain an audit trail of all log-ins, edits, and log-outs. Data collected on the tablets can be recorded with or without an internet connection. When there is a connection, the data will be automatically uploaded to the secure study server that will require password authentication. When there is not an internet connection, the data will be cached on the tablet and automatically upload once an internet connection is established. The data will be automatically deleted from the tablet once the upload to the study server is complete and the server will send an automatic email to the project manager and PI indicating that new data have been uploaded. Access to the data collected on the tablets and stored on the study server will be limited to only those study personnel with data access rights. The project manager will monitor the study server weekly to ensure that the data collected and uploaded to the server are complete and to monitor for suspicious data activity.

Data from source 3 (EMD data) and source 4 (mobile app data) will be stored on remote, password protected secure servers and contain no personally identifiable information.

Data from source 5 (biospecimens) will be identified only by the unique PID. Viral load results will be entered into the AIDS Center electronic medical record by clinic staff once the sample is processed. AIDS Center staff will provide a GHRCCA RA with study participant viral load results. DBS results will be processed at the University of Colorado. Hair sample results processed at the University of California-San Francisco.

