6.4. Adverse Events

Serious adverse events include death, a life-threatening event, or an event resulting in hospitalization, prolongation of hospitalization, and disability. Serious adverse events, regardless of whether or not they are study-related, will be reported to the Columbia University IRB and the IRB at the study site serving the participant. Other adverse events include breaches of confidentiality (both intentional – e.g., mandated reporting of suicidal/homicidal participants – and unintentional), and non-life threatening psychological distress, arrest by the police and violence. The PI and research staff will closely monitor adverse events. The research team is aware that the study sample is likely to experience some adverse events, though unlikely to be study-related, due to their status in Kazakhstani society, their current or past history of law-breaking activity (e.g., use of or selling of illegal drugs), and the high levels of service needs. Drawing upon past GHRCCA studies, the research team designed an adverse event form.

Study staff will identify, manage and document all adverse events. These events may be identified by RAs, the Project Manager, or other staff, or they may be reported by participants. The procedures used to track, report, and examine adverse events are described below.

- 1) After an adverse event is reported/detected, the study staff member who identified the event will complete an Adverse Event Report form. The report form will include the date, description of the event, duration, severity, measures taken to ameliorate the adverse event, and disposition-related information (e.g., time spent providing referrals and type of referral). The report form will be reviewed and signed by the project manager, [name], and [name], who will be responsible for ensuring that appropriate actions have been taken.
- 2) Drs. [name] and [name] will consult with the Project Manager and any involved staff to ascertain whether the event was related to participation in the study and to ensure that an adequate response is provided to the participant. This will be followed by submission of a report to the IRBs at Columbia University and the Al-Farabi Kazakh National University.

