- 3) In the event that a participant withdraws from the study or the PI decides to discontinue a participant due to an adverse event, the participant will be monitored by the Project Manager and the PI via ongoing status assessment until (a) a resolution is reached or (b) the event is determined to be unrelated to the study intervention.

Every two months, the research team from Columbia University and GHRCCA will review all adverse event data to date to determine if systematic trends exist among adverse event data to warrant changes to study protocols and procedures. Any proposed changes will be reviewed with staff at the study site, and, if needed, an external consultant (e.g., other senior investigators conducting federally-funded research on drug abuse). Approval for changes in study protocol or materials will then be obtained from the IRBs at Columbia University and the Kazakhstan School of Public Health. After approval, the NIDA Project Scientist will be notified, and changes will also be reported in the annual progress report submitted to NIDA.

6.4.1. Psychological distress. Participants may experience psychological distress resulting from the assessment questions. Using strategies established in our previous studies, the following steps will be taken to minimize the risk of psychological distress resulting from assessment questions.

1. Participants will be informed that the assessments include questions about sensitive behaviors (e.g., mental health, drug use, sexual behaviors, non-adherence), and that they can decline to answer any questions with which they are uncomfortable.
2. Procedures for emergency and nonemergency situations will involve the RA interviewer informing the project manager and PI of any such incidents of distress so that s/he can monitor compliance with distress-related protocol.
3. Participants who experience mild to moderate distress will be referred to the AIDS Center mental health staff for counseling. We will be able to make immediate referrals as needed to health care providers.

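### Distress from the assessment questions is reported by an RA interviewer, but surveys are self-completed in Qualtrics and a weekly app, so it may be under-detected

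*Protocol*

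**What the plan says.** **The risk and its safeguard.** Protocol 6.4.1 states: "Participants may experience psychological distress resulting from the assessment questions". It lists three steps. Step 1 warns participants about sensitive topics and lets them decline questions. Step 2 is the reporting step: "Procedures for emergency and nonemergency situations will involve the RA interviewer informing the project manager and PI of any such incidents of distress". It also refers to a protocol on distress that is not set out in these documents. Step 3 begins "Participants who experience mild to moderate distress will be referred to the AIDS Center mental health staff for counseling" and then adds that staff can refer to health care providers at once where needed, with no limit by severity.

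**How assessments are given.** Protocol 4.3.1 says "the RA will send the participant a Qualtrics link to complete the baseline assessment". Sections 4.6.1, 4.6.3 and 4.6.4 likewise have the RA send the survey, and 4.6.5 says "Study assessments will be delivered remotely through Qualtrics". Section 4.6.7 adds weekly surveys through a phone app on drug use, adherence, social support and relationship satisfaction.

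**Other contact and reporting.** The four assessment visits take place by phone or video call, or in person. Section 6.4 classes non-life-threatening psychological distress as an adverse event and allows RAs, the project manager, other staff or participants to bring events to light. Section 4.6.11 assesses intervention safety through adverse event reports from study and clinic staff and an exit interview. On data review, section 5 says "The project manager will monitor the study server weekly", for completeness and suspicious activity.

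**The concern.** The safeguard is written for an interviewer who puts the questions and sees the reaction. The procedures describe someone who sends a link. If the RA is not in contact while the survey is being filled in, or soon after, the person expected to start the reporting chain may have nothing to report. The weekly app is the clearest case, because no staff member is described as taking part.

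Two things are at stake. The first is participant protection, for a risk that the protocol itself names. The second is interpretation: safety is part of Aim 2 and is assessed largely through adverse event reports, so a low count of distress events could mean either that few occurred or that few were seen.

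**Working it through.** No figure in the plan depends on this point, so the check sets the sections side by side.

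**1. Trigger against mode of delivery.**

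| Section | What it describes |
|---|---|
| 6.4.1, step 2 | An RA interviewer reports distress, in emergencies and otherwise |
| 4.3.1, 4.6.1, 4.6.3, 4.6.4 | The RA sends a Qualtrics survey; the participant completes it |
| 4.5 | Baseline survey completed at the baseline visit, held by phone or computer |
| 4.6.5 | Assessments delivered remotely |
| 4.6.7 | Weekly app surveys; no staff role in completion |
| 5 | Assessment data collected on tablets, online or offline |

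Sections 4.6, 5 and 6.4.1 therefore give three different pictures of how assessments are administered. Section 4.2 adds "Due to COVID-19, all study procedures will be conducted remotely", while 4.6.1, 4.6.3 and 4.6.4 also allow in-person visits.

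**2. Does another step reveal distress during self-completion?**
- *RA contact at visits.* It exists, but no section asks the RA to stay in contact during completion or to ask about distress afterwards.
- *Reporting routes in 6.4.* These say who may raise an event. They add no step that would bring one to light.
- *Weekly server check in section 5.* Its stated purpose does not include reading answers for distress.
- *Exit interview in 4.6.11.* It follows the 6-month visit and asks about negative experiences of the intervention, which is not the same as distress from questionnaires.

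Each route could catch an event. None is designed to.

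**3. Exposure (a ceiling, not an estimate of missed events).**
- Main surveys: 66 dyads × 2 = 132 people; 132 × 4 occasions = 528 completions. This assumes no dropout. Completions in person or on a call may be observed.
- Weekly app: 180 days ÷ 7 ≈ 26 surveys per person, using the 180-day window in SAP 4.2. If follow-up instead runs six months from the end of the intervention (protocol 4.2), and the sessions take one to two months, the figure is 210 ÷ 7 = 30 to 240 ÷ 7 ≈ 34.

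The documents give no rate of distress and no chance of detection, so the number of missed events cannot be computed.

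**4. Severity and response.** Mild to moderate distress has a named destination, the AIDS Center mental health staff. For anything more severe, the text offers onward referral where needed and the reporting line in step 2, but names no destination. The protocol on distress mentioned in step 2 may do so; it cannot be checked here.

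**The case against.** The strongest reply is that the protocol is silent on observation rather than contradictory. Section 4.5 places baseline completion within the visit. At baseline, IPI and 3 months, sending the survey sits in the procedure list between the locator form and RA contact about the monitoring device, so the RA may well be on the line. Staff and participants can report distress by other routes, and participants also meet AIDS Center nurses. The warning and the right to decline need no observer. The app does not ask about mental health or sexual behaviour. All of this stands, and it limits the point to possible under-detection.

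A reader might infer four stronger things that the documents do not support:
- *That referral covers only mild to moderate distress.* The next sentence of step 3 allows immediate referral with no severity limit, and step 2 includes emergencies.
- *That the protocol expects suicidal or homicidal participants and leaves them without a route.* Section 6.4 mentions "mandated reporting of suicidal/homicidal participants" only as an example of an intentional breach of confidentiality. The expectation it states is of some adverse events in general.
- *That the distress count will be close to zero by design.* The other reporting routes make that unsupported.
- *That every survey should be supervised.* That would cost RA time and might change answers about drug use or non-adherence. The gap can be narrowed without it.

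**Conclusion.** The mismatch is real and worth correcting. Section 6.4.1 relies on an RA interviewer, while the operating sections describe self-completed Qualtrics surveys and a weekly app. No step is designed to show distress during self-completion, so events may be under-detected and a low count would be weak evidence of safety. The point is strongest for the app and weaker at visits where the RA happens to be on the line.

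On severity, the supportable statement is narrow: only mild to moderate distress has a named destination, and the separate protocol that might complete the picture is not in these documents.

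The conclusion rests on the text as written. If the RA in practice stays on the call until the survey is finished and then asks how the participant is, most of the gap at visits closes, but the protocol should say so. The size of any under-count is unknown.

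**What to change.** 1. **Reconcile protocol 4.6, 5 and 6.4.1** on how assessments are given (Qualtrics link, tablet, call or in person) and how distress is detected. Replace the reference to an interviewer with the role that actually applies.
2. **Add one brief RA distress check** after the survey is completed at the baseline, IPI, 3-month and 6-month visits. The RA need not see the answers or watch completion.
3. **Add a closing distress item** to the Qualtrics surveys, and to the weekly app where feasible, with an automatic alert to the project manager and PI.
4. **Reconcile 6.4 and 6.4.1** on who responds at each severity, and attach or cite the protocol on distress that step 2 mentions. The sponsor decides the clinical route.

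The SAP describes the pilot in the past tense. If data collection is over, the safety report should state how surveys were actually completed and how distress was detected, and the planned full-scale trial should carry the corrected text.

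The cost is a wording change, a survey setting, slightly longer RA calls and some alerts to handle.

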6.5. Alternatives

Participation in the study is voluntary and participants may withdraw from the study at any time. There are no alternatives to participation. Participants are free not to participate or to withdraw at any time. Their treatment will not be affected in any way, and they may still continue to attend the clinic.

6.6. Benefits

Study participants will receive no direct benefits from participating in this study. The potential benefit to science and society is documented evidence that a couples-based ART adherence intervention can be used to improve ART adherence among HIV-positive individuals. This can help patients better manage their health and minimize the disruptions and negative health consequences caused by non-adherence to ART.

6.7. Compensation

Compensations will be based on those routinely offered at the study site for this type of research. Participants in 2-hour focus groups will receive approximately \$30 USD for their time and effort. Participants completing each assessment visit will receive approximately \$15-20 USD to compensate for time and biosampling. Intervention participants will receive \$10-15 USD for each intervention session. Participants will also receive a bonus incentive (approximately \$35) for returning their EMD device, and an additional small incentive (\$1 USD) for each weekly survey they complete.

6.8. Participant Privacy and Confidentiality. All participant-related data, including biospecimens, assessment data, EMD output, mobile app survey data, and participant files will be kept strictly confidential. All data and records will be labeled only with PIDs, and no participant names will be attached to study data. The participant "key" linking study identification numbers with participant names will be kept by the project manager in locked file cabinets at GHRCCA offices. Only the project manager/PI will have access to this "key" and file cabinets. Personal information including participant's name, address and phone number will be stored separately from research data. Electronic data files will be password protected and stored on the study server, which requires authentication to access. All paper research data will be kept in locked file cabinets and will be available only to research staff directly involved in this project and institutional personnel for the purpose of routine audits. All study staff are trained on procedures to protect participant confidentiality and will take all required courses and certification tests. Participants will be told that all data are confidential within the limits of the law.

## 1. INTRODUCTION

The SMART Couple II study was designed to adapt a couples-based antiretroviral therapy (ART) adherence intervention for HIV-positive people who inject drugs (PWID) in Kazakhstan and their treatment support partners. The adapted intervention was then pilot tested among 66 HIV-positive PWID and their treatment support partners (n=66) to assess the feasibility and acceptability of the intervention and obtain preliminary estimates of adherence outcomes in the intervention arm versus the standard of care arm.

This document outlines the statistical analysis plan that will be followed to assess the adherence outcomes.

**Primary Outcome:** To evaluate the difference in ART adherence as measured through an electronic monitoring device (EMD) throughout the six-month follow-up between the intervention and standard of care arms.

**Secondary Outcome 1:** To evaluate the difference in biological measures of ART adherence (e.g., viral load, hair samples, dried blood spot testing) between the intervention and standard of care arms.

**Secondary Outcome 2:** To evaluate the difference in self-reported ART adherence as measured through a validated three-item adherence scale at the six-month follow-up between the intervention and standard of care arms.

**Secondary Outcome 3:** To evaluate the difference in uptake of opioid substitution therapy (OST) at the six-month follow-up between the intervention and standard of care arms.

